3.2 END OF STUDY AND LENGTH OF STUDY

The end of this study is defined as the date when all patients have completed the study completion or early termination visit, or have otherwise been discontinued from the study. The total duration of this study for each patient is approximately 62 weeks, including screening, run-in, treatment, and follow-up.

In addition, the Sponsor may decide to terminate *enrollment or the entire study* at any time.

The total length of the study, from screening of the first patient to the end of the study, is expected to be approximately 25 months.

3.3 RATIONALE FOR STUDY DESIGN

3.3.1 Rationale for MTPS9579A Dose and Schedule

The dose of MTPS9579A in this study (1800 mg IV Q4W) has been selected by the Sponsor based on the totality of the following data: understanding of tryptase biology in healthy volunteers and patients with asthma, Phase Ia/b SAD/MAD clinical trial data, MTPS9579A properties, mechanism of action, nonclinical activity and safety, and prior clinical experience targeting tryptase. The selected Phase IIa dose is within the dose range previously evaluated in the Phase Ia/b study (GA40396). In that study, doses up to 3600 mg of MTPS9579A administered intravenously as a single dose or as a Q4W regimen (3 doses), which was the maximum dose tested, was well tolerated. The dose and regimen to be tested in this study (1800 mg IV Q4W) is projected to maximize the potential for clinical benefit based on the totality of data available to date. At steady-state concentrations, it is anticipated that this dose will reduce active tryptase levels by 95%, which accounts for the maximum concentration of active tryptase that may be present in the airway of patients with asthma while ensuring patient safety. More details on the safety, PK, and PD activity of MTPS9579A are available in the MTPS9579A Investigator's Brochure.

3.3.2 Rationale for Patient Population

The current high unmet medical need in asthma is for patients with uncontrolled disease despite adherence to guidelines-based, standard-of-care therapy. In this study, the target population is patients with moderate to severe asthma whose disease remains uncontrolled despite daily use of ICS therapy and at least one additional controller medication. Patients must have a diagnosis of asthma, an Asthma Control Questionnaire, 5-item version (ACQ-5) score ≥ 1.5 ([Appendix 2](#)), and have experienced at least two asthma exacerbations (as defined in Section [4.1.1.1](#)) within the 12 months prior to screening as evidence of uncontrolled disease.

Patients with uncontrolled asthma despite treatment represent a high unmet medical need because they have exhausted conventional therapeutic options. A recent study has demonstrated that patients with a history of exacerbations are at the highest risk for future exacerbations (Bloom et al. 2018). Therapeutic options for these patients are limited because of the heterogeneity of clinical response to controller medications and the substantial side effects of high-dose ICS and oral corticosteroid therapy (Wong et al. 2000; Holt et al. 2001; Suissa et al. 2002; Szeffler et al. 2002; Masoli et al. 2004a, 2004b, 2005; Adams and Jones 2006; Sears et al. 2009; Lemanske et al. 2010).

The National Heart, Lung, and Blood Institute Expert Panel Report 3 (2007) and Global Initiative for Asthma (2018) guidelines include several options for the addition of controller medications, including LAMAs (e.g., tiotropium), which reflect the heterogeneity of clinical response to each medication class (Lemanske et al. 2010). Consequently, the protocol-defined additional controller medications include LABAs, LTM/LTRAs, and LAMAs. While individuals in this population with eosinophilic asthma respond favorably to treatment with biologic-based therapies modulating eosinophil-related signaling pathways (IL-5, IL-4/IL-13), these therapies are of limited benefit to patients with asthma who have lower levels of eosinophils.

3.3.3 Rationale for Control Group

A placebo-treated control group will be used in this study to assess differences in CompEx events, pulmonary function, asthma control, symptoms, PD biomarkers, and safety in patients who receive MTPS9579A compared with patients who receive placebo. The use of a control group is necessary to assess safety signals that may be attributable to MTPS9579A in a patient population and given the inherent variability in symptoms and lung function. Patients in the control group will undergo the same study assessments as patients treated with MTPS9579A. All patients will continue to receive standard-of-care treatment for asthma and other allowable medical conditions (with some restrictions; refer to Section [4.4](#)) in addition to study drug (MTPS9579A or matching placebo) throughout the study.

3.3.4 Rationale for Biomarker Assessments

Biomarker assessments, before and at various timepoints after treatment, will be used to demonstrate evidence of the biologic activity of MTPS9579A in patients, identify biomarkers that may be predictive of response to MTPS9579A, define PK/PD relationships, support selection of a recommended dose regimen, advance the understanding of the mechanism of action of MTPS9579A in patients, and increase the knowledge and understanding of disease biology. During this study, urine samples, serum samples, blood samples, and upper airway samples will be collected.

Nasosorption is an upper airway, non-invasive sampling method that uses a synthetic absorptive matrix to collect nasal mucosal lining fluid from the nose.

Blood samples will be collected for DNA extraction to enable identification of mutations in genes encoding tryptase (*TPSAB1* and *TPSB2*) that are associated with tryptase levels and activity in the airway or can increase the knowledge and understanding of disease biology.

3.3.5 Rationale for Optional Methacholine Challenge Test

Mast cell microlocalization within airway smooth muscle cell bundles is thought to contribute to airway hyper-responsiveness (Brightling et al. 2002). Methacholine challenge testing, a measure of airway hyper-responsiveness, will be used to demonstrate physiological activity of MTPS9579A in patients. This assay will be examined with PK/PD and biomarker data to understand the mechanism of action of MTPS9579A.

4. MATERIALS AND METHODS

4.1 PATIENTS

Approximately 160 patients with moderate to severe asthma *were originally planned to be randomized in this study (80 patients in each of 2 treatment arms); however, as of August 2021, study enrollment has been halted with 134 patients enrolled.*

4.1.1 Inclusion Criteria

4.1.1.1 Inclusion Criteria for Enrollment in the Run-In Period

Patients must meet the following criteria for enrollment in the run-in period:

- Signed Informed Consent Form
- Ability to comply with the study protocol, in the investigator's judgment
- Age 18–75 years, inclusive, at the time of signing the Informed Consent Form
- Body mass index of 18–38 kg/m² and weight \geq 40 kg at screening
- Documented physician-diagnosed asthma for at least 12 months prior to screening
- Pre-bronchodilator FEV₁ 40%–80% predicted at screening

- Post-bronchodilator reversibility of FEV_1 (liters) $\geq 12\%$ and ≥ 200 mL at screening

Post-bronchodilator reversibility testing, including medication-withholding strategies and appropriate dosing of short-acting bronchodilators, should be performed per American Thoracic Society (ATS)/European Respiratory Society (ERS) guidelines (Miller et al. 2005).

Alternative evidence demonstrating variable expiratory airway limitation may be considered after discussion with the Medical Monitor.
- Treatment with asthma controller therapy (daily ICS [≥ 100 μg of fluticasone propionate or equivalent] and at least one additional controller therapy [LABA, LAMA, LTM/LTRA]) for ≥ 3 months prior to screening, with no changes within 4 weeks prior to screening or during the screening period and no anticipated changes in controller dosing regimens throughout the study

For patients receiving a total daily ICS dose of < 500 μg fluticasone propionate or equivalent, one of their additional controller therapies must be LABA.

For patients receiving a total daily ICS dose of ≥ 500 μg fluticasone propionate or equivalent, they must receive one or more of the following additional controller therapies: LABA, LTM/LTRA, LAMA, or long-acting theophylline preparations.
- ACQ-5 score ≥ 1.5 at screening
- Documented history (e.g., medical report, pharmacy prescription assessed by investigator) of ≥ 2 asthma exacerbations within the 12 months prior to screening while on daily ICS maintenance therapy, defined as new or increased asthma symptoms (wheezing, coughing, dyspnea, chest tightness, and/or nighttime awakenings due to these symptoms) that result in at least one of the following:
 - Hospitalization or an emergency department or urgent care visit with systemic corticosteroid treatment
 - Use of systemic (IV, IM, or oral) corticosteroids for ≥ 3 days or a long-acting depot corticosteroid preparation with a therapeutic effectiveness of ≥ 3 days
- Demonstration of acceptable inhaler, peak flow meter, and spirometry techniques at screening
- Demonstrated compliance with required use of the eDiary, defined as completing all required assessments (answering questions related to asthma symptoms, PEFR measurements, and use of short-acting rescue therapy) on at least 5 of 7 days during each of 2 consecutive weeks within the screening period (12–28 days)
- For women of childbearing potential: agreement to remain abstinent (refrain from heterosexual intercourse) or use contraception, as defined below:

Women must remain abstinent or use contraceptive methods with a failure rate of $< 1\%$ per year during the treatment period and for 60 days after the final dose of MTPS9579A.

A woman is considered to be of childbearing potential if she is postmenarcheal, has not reached a postmenopausal state (≥ 12 continuous months of

amenorrhea with no identified cause other than menopause), and is not permanently infertile due to surgery (i.e., removal of ovaries, fallopian tubes, and/or uterus) or another cause as determined by the investigator (e.g., Müllerian agenesis). The definition of childbearing potential may be adapted for alignment with local guidelines or regulations.

Examples of contraceptive methods with a failure rate of <1% per year include bilateral tubal ligation, male sterilization, hormonal contraceptives that inhibit ovulation, hormone-releasing intrauterine devices, and copper intrauterine devices.

The reliability of sexual abstinence should be evaluated in relation to the duration of the clinical trial and the preferred and usual lifestyle of the patient. Periodic abstinence (e.g., calendar, ovulation, symptothermal, or postovulation methods) and withdrawal are not acceptable methods of contraception. If required per local guidelines or regulations, locally recognized acceptable methods of contraception and information about the reliability of abstinence will be described in the local Informed Consent Form.

- For men: agreement to remain abstinent (refrain from heterosexual intercourse) or use a condom, and agreement to refrain from donating sperm, as defined below:

With a female partner of childbearing potential or pregnant female partner, men must remain abstinent or use a condom during the treatment period and for 60 days after the final dose of MTPS9579A to avoid exposing the embryo. Men must refrain from donating sperm during this same period.

The reliability of sexual abstinence should be evaluated in relation to the duration of the clinical trial and the preferred and usual lifestyle of the patient. Periodic abstinence (e.g., calendar, ovulation, symptothermal, or postovulation methods) and withdrawal are not acceptable methods of preventing drug exposure. If required per local guidelines or regulations, information about the reliability of abstinence will be described in the local Informed Consent Form.

4.1.1.2 Inclusion Criteria for Enrollment in the Double-Blind Treatment Period

After completing the run-in period, patients must meet the following additional criteria for enrollment in the double-blind treatment period:

- Ongoing compliance with required use of the eDiary, defined as completing all required assessments (answering questions related to asthma symptoms, PEFR measurements, and use of short-acting rescue therapy) on at least 5 of 7 days during each of the 2 consecutive weeks of the run-in period
- No changes in ICS therapy or allowed controller medications (see Section 4.1.1.1) during the run-in period
- No new asthma exacerbation or infection (defined in Section 4.1.2) during the run-in period

4.1.1.3 Inclusion Criteria for the Optional Methacholine Challenge Test

Patients enrolled in the double-blind treatment period must meet the following additional criteria for enrollment into the optional methacholine challenge test:

- Signed Informed Consent Form for the Optional Methacholine Challenge Test
- Methacholine challenge at randomization ($PD_{20} \leq 200 \mu\text{g}$)
- $\text{FEV}_1 60\%-80\% \text{ predicted}$

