4.5.14 Optional Methacholine Challenge Test

Consenting patients who meet additional inclusion criteria (Section 4.1.1.3) will undergo an optional methacholine challenge test, which should be performed before study drug dosing and within the visit windows for randomization and the Week 30 visit.

Methacholine challenge will be performed using standard techniques (Coates et al. 2017) and as described in the study PFT manual.

The Informed Consent Form will contain a separate section that addresses this optional test. A separate, specific signature will be required to document a patient's agreement to undergo optional testing. The investigator should document whether the patient has given consent to participate and (if applicable) the date(s) of consent, by completing the Optional Methacholine Challenge Test Informed Consent eCRF.

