5.2.4 Selected Adverse Events

Additional data will be collected for the following selected adverse events:

- Adverse event information related to the predose optional methacholine challenge test should only be collected if it is a serious adverse event (see Section 5.3.1).
- Adverse event information related to the optional Week 30 methacholine challenge test should be collected and the relatedness to the procedure should be captured in the appropriate eCRF.

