5.3.1 Adverse Event Reporting Period

Investigators will seek information on adverse events at each patient contact. All adverse events, whether reported by the patient or noted by study personnel, will be recorded in the patient's medical record and on the Adverse Event eCRF.

After informed consent has been obtained but prior to initiation of study drug, only serious adverse events caused by a protocol-mandated intervention (e.g., invasive procedures such as biopsies, discontinuation of medications) should be reported (see Section 5.4.2 for instructions for reporting serious adverse events).

After initiation of study drug, all adverse events will be reported until 12 weeks after the final dose of study drug or until discontinuation from the study, whichever occurs later. However, for patients who receive placebo during run-in but fail to be randomized, adverse events will be reported only until 6 weeks after the placebo dose. After this period, the Sponsor should be notified if the investigator becomes aware of any serious

adverse event that is believed to be related to prior study drug treatment (see Section 5.6).

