5.4.2 Reporting Requirements for Serious Adverse Events and Adverse Events of Special Interest

5.4.2.1 Events That Occur prior to Study Drug Initiation

After informed consent has been obtained but prior to initiation of study drug (including single-blinded placebo during the run-in), only serious adverse events caused by a protocol-mandated intervention should be reported. The paper Clinical Trial Serious Adverse Event/Adverse Event of Special Interest Reporting Form provided to investigators should be completed and submitted to the Sponsor or its designee immediately (i.e., no more than 24 hours after learning of the event), either by faxing or by scanning and emailing the form using the fax number or email address provided to investigators.

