Appendix 1: Schedule of Activities

ACQ-5=Asthma Control Questionnaire (5 items); ADA=anti-drug antibody; eDiary=electronic diary; EOT=end of treatment; ET=early termination; FeNO=fractional exhaled nitric oxide; PBO=placebo; PEFR=peak expiratory flow rate; PK=pharmacokinetic; PPD=purified protein derivative; Rand.=randomization; SNP=single nucleotide polymorphism; TB=tuberculosis; UV=unscheduled visit; WGS=whole genome sequencing.

Notes: On treatment days, all assessments should be performed prior to study drug dosing, unless otherwise specified.

- ^a The screening period may last up to 4 weeks. The earliest a patient can qualify for the run-in period is after 12 days, when eDiary compliance criteria are met. Patients are allowed one attempt to re-screen.
- ^b Run-in takes place from Day 1 through Day 14 to assess baseline eDiary symptoms; however, these assessments must be performed on Day 1 (± 2 days).
- ^c Note that these tests occur on the same day, before (left column) or after (right column) the patient has been randomized.
- ^d Patients who complete the treatment period will return to the clinic for a treatment completion visit at Week 50. Patients who discontinue study drug for any reason should continue follow-up for all remaining study visits through the end of the study.
- ^e Final safety follow-up will be conducted by telephone call.
- ^f Patients who experience symptoms consistent with an asthma exacerbation will be asked to come to the clinic for an unscheduled visit for additional evaluations. Assessments should be performed as clinically indicated.
- ^g Patients who are randomly allocated to the 48-week double-blind treatment period but discontinue study drug should continue follow-up for all other study procedures and measurements through the end of the study, except for collection of serum and nasosorption samples for biomarkers.
- ^h Informed consent must be documented before any study-specific screening procedure is performed.
- ⁱ Includes evaluation of the head, eyes, ears, nose, and throat, and the cardiovascular, dermatologic, musculoskeletal, respiratory, gastrointestinal, and neurologic systems.

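### Protocol 5.2.4 drops non-serious adverse events of the randomization-visit methacholine challenge, although that visit already lies inside the all-adverse-event reporting window

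*Protocol*

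**What the plan says.** **Timing of the test.** Protocol 4.1.1.3 requires "Methacholine challenge at randomization" for entry to the optional substudy. Section 4.5.14 describes a test that "should be performed before study drug dosing and within the visit windows for randomization and the Week 30 visit". A note to the randomization column in Appendix 1 reads "Note that these tests occur on the same day, before (left column) or after (right column) the patient has been randomized", and the first double-blind infusion is given at the same visit (Week 2).

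**Collection rule for the first test.** Section 5.2.4 states "Adverse event information related to the predose optional methacholine challenge test should only be collected if it is a serious adverse event" and refers to 5.3.1.

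**Collection rule for the second test.** The next bullet of 5.2.4 says the opposite: "Adverse event information related to the optional Week 30 methacholine challenge test should be collected". Relatedness to the procedure is captured as well.

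**Reporting window.** Section 5.3.1 provides "After initiation of study drug, all adverse events will be reported until 12 weeks after the final dose of study drug" or later. Section 5.4.2.1 says what counts as the start, describing the earlier period as "prior to initiation of study drug (including single-blinded placebo during the run-in").

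**Related rules.** The adverse event definition in 5.2.1 gives the methacholine challenge as an example of a protocol-mandated intervention whose events count. Section 5.3.5.1 asks that events from the start of an infusion to 24 hours afterwards be entered on the adverse event form as separate signs and symptoms.

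**The concern.** Section 5.2.4 treats the randomization-visit challenge as if study drug had not yet started. By the protocol's own definition it started at Week 0. A class of events that the reporting section requires is therefore not collected, and the section cited in support does not support it.

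A second problem follows from how the limit is worded. It is defined by relatedness to the test and has no end time. Section 5.1.1.2 lists cough, dyspnea, wheeze and bronchospasm among the signs of systemic reactions to antibodies, usually appearing during dosing or within hours. These overlap with the effects of methacholine, so attribution is least certain exactly where the rule depends on it. Section 1.3 says that risks in patients with asthma are unknown, so mild respiratory events around the first double-blind dose are worth having complete.

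**Working it through.** The plan states no figure on this point. The check is a comparison of dates and rules, followed by arithmetic for scale only.

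**1. Is the challenge inside the all-event window?** Appendix 1 puts the run-in placebo on Day 1 and randomization on Day 15 (±2).
- Nominal interval: 15 − 1 = 14 days.
- Range with placebo on Day 1: 13 − 1 = 12 to 17 − 1 = 16 days.

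Under 5.4.2.1 the placebo is study drug, so the window in 5.3.1 is open before the challenge at any point in this range. Three other places agree:
- 5.3.1 follows patients who fail run-in for adverse events until 6 weeks after the placebo dose.
- 6.5 plans a safety analysis of the run-in.
- The adverse event row of Appendix 1 is marked at run-in and on both sides of randomization.

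**2. Does 5.3.1 support a serious-only rule here?** Its serious-only provision covers the time between consent and study drug. That period ended at Week 0. The cross-reference in 5.2.4 therefore points to a rule that no longer applies at Week 2.

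**3. Which events are dropped?**

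| Non-serious event | 5.2.4 | Other sections |
|---|---|---|
| After the Week 2 challenge, before the infusion, related to the test | not collected | 5.2.1 and 5.3.1: an adverse event, to be reported |
| After the Week 2 infusion starts, attributed to the test | not collected (no time limit) | 5.3.5.1: record signs and symptoms up to 24 hours after dosing |
| Related to the Week 30 challenge | collected | 5.3.1: to be reported |

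The first row is a direct contradiction and needs no misattribution. In the second row a site has two instructions that disagree, and the outcome depends on which one it follows.

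**4. Scope.** Section 3.1 plans about 20 substudy patients per arm. SAP Output 1.1 shows 134 dosed patients, 69 of them active.
- All patients: 40 / 134 = 30%.
- Active arm: 20 / 69 = 29%.

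Both assume that the substudy filled as planned. Actual uptake is not given.

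**5. Possible size of a post-infusion loss.** The documents give no rate p of mild respiratory events at the first double-blind infusion, so p is assumed. Among 20 active substudy patients, the expected number is 20p and the chance of at least one is 1 − (1 − p)^20.

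| Assumed p | Expected events | P(at least one) |
|---|---|---|
| 1% | 0.2 | 0.18 |
| 5% | 1.0 | 0.64 |
| 10% | 2.0 | 0.88 |
| 20% | 4.0 | 0.99 |

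These are ceilings. An event is lost only if the site also attributes it to methacholine and follows 5.2.4 over 5.3.5.1. The floor is zero.

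**The case against.** A reader might infer that mild bronchospasm after the first double-blind infusion will go unrecorded in these patients. The documents do not support that, for several reasons:
- Section 5.3.5.1 calls for recording events within 24 hours of dosing and makes no exception for methacholine.
- Table 4 presumes that an event is related to study drug unless another cause or implausible timing is shown.
- Section 5.1.1.2 requires patients to be clinically stable before each dose, judged partly by spirometry or peak flow. This makes it harder to blame methacholine afterwards.
- Appendix 1 schedules serial vital signs and focused examinations through the infusion and the hour after it.
- Section 4.5.14 allows the test anywhere in the visit window before dosing, so a same-day sequence is what the schedule implies but is not certain.

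These points reduce the harm to a risk. They do not remove the conflict. Section 5.3.5.1 mainly governs the form of the entry (signs rather than a diagnosis) and does not say that it overrides 5.2.4, which is the specific rule for this test. The presumption in Table 4 can be rebutted by evidence of another cause, and a provocation test given shortly before is an obvious candidate. The special-interest route in 5.2.3 catches allergic reactions only from Grade 3, and the WHO scale grades bronchospasm as a separate item.

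A second objection is that predose challenge effects are expected, and that 6.5 leaves them out of the double-blind treatment-emergent summaries. That is correct. Restoring them would not change those tables, but 5.3.1 still requires them to be reported.

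A reader might also infer that a comparison of the two challenge tests is spoiled. Neither the protocol's safety analyses nor the SAP's safety outputs plan one.

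**Conclusion.** The inconsistency is established from the text alone. Section 5.2.4 excludes non-serious events of the Week 2 challenge that 5.2.1 and 5.3.1, read with 5.4.2.1, require, and it treats the Week 30 challenge in the opposite way. The loss of a mild respiratory event after the infusion is possible, not directed: it needs a site to attribute the event to methacholine and to apply 5.2.4.

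The size is small. At most the planned substudy of about 20 patients per arm is affected, and uptake is unknown. The rule is the same in both blinded arms, so its main effect would be to lower the recorded count of mild events around that dose. The expected numbers of 0.2 to 4.0 rest entirely on assumed rates of 1% to 20% and are upper limits; the true number may be zero. The point merits correction because it is a safety-collection rule that contradicts the protocol's own reporting window and because the repair is cheap.

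**What to change.** Reconcile 5.2.4 with 5.3.1, 5.4.2.1 and 5.3.5.1:
- Remove the serious-only limit and apply the Week 30 collection rule to both challenges.
- Record onset time relative to the challenge and to the start of infusion, with relatedness to study drug and to the procedure as separate items.
- State that any event starting once the infusion has begun is recorded, whatever its attribution.

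Enrollment is permanently closed, so the change works mainly through data already in source. If the database is not locked, query substudy sites for adverse events noted on the randomization day and enter them. If it is locked, state in the study report that non-serious events attributed to this challenge were not collected.

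The cost is a short change to 5.2.4 and a query covering about 40 patients if the substudy filled. Source notes may be incomplete, because sites were told not to collect these events. Expected, transient methacholine symptoms will now be recorded and should be flagged as procedure-related; those starting before the infusion stay outside the double-blind treatment-emergent tables under 6.5.
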